7.4.4. Clinical Site Reporting: Notifying the Methods Centre	20
7.4.5. Clinical Site: Institutional Review Board and Research Ethics Board Reporting.....	20
7.5. Dissemination Policy.....	20
References.....	21

LIST OF ABBREVIATIONS

Abbreviation	Explanation
AROM	Active Range of Motion
ASES	American Shoulder and Elbow Surgeons
CEO	Centre for Evidence-Based Orthopaedics
CRF	Case Report Form
CI	Confidence Internal
DSMC	Data and Safety Monitoring Committee
EDC	Electronic Data Capture
ER	External Rotation
FTD	First-Time Dislocation
HiREB	Hamilton Integrated Research Ethics Board
ICF	Informed Consent Form
IR	Internal Rotation
IRB	Institutional Review Board
ISIS	Instability Severity Index Score
MRI	Magnetic Resonance Imaging
NISIS	Non-Operative Instability Severity Index Score
PE	Physical Examination
PHI	Personal Health Information
PNF	Proprioceptive Neuromuscular Facilitation
PROM	Passive Range of Motion
PT	Physical Therapy
RCT	Randomized Controlled Trial
REB	Research Ethics Board
SAE	Serious Adverse Event
WOSI	Western Ontario Shoulder Instability
WSIB	Workplace Safety & Insurance Board

STUDY SUMMARY

Study Design	Randomized Controlled Trial with Embedded Non-randomized Cohort
Coordinating Centre	McMaster University, Department of Surgery Clinical Trials Unit, in collaboration with St. Joseph's Hospital, department of Surgery.
Background	
The shoulder is the most commonly dislocated joint in the body with a global incidence that ranges from 15 to 25 per 100 000 people. The estimated annual societal cost in North America due to first-time shoulder dislocations exceeds \$1.2 billion CAD.
 
Anterior dislocations, the most common type of shoulder dislocation, are often complicated by subsequent instability and recurrent dislocation, with reported rates as high as 47%. Shoulder instability commonly results in pain and negatively impacts quality of life.
 
Current standard of care suggests surgical stabilization of the shoulder after two or more dislocations, but the evidence is far from conclusive. Observational studies suggest that early surgical stabilization has strong biological rationale in limited risks of recurrent dislocation, improving quality of life, and potentially decreasing the future risk of shoulder arthritis. Also, some economic health studies suggests that surgery is less costly and more effective, even after recurrent dislocations.

Objective of the Pilot Study	The primary objective of the pilot study is to assess the feasibility of a definitive trial to determine the effect of arthroscopic soft tissue stabilization vs. non-surgical treatment on rates of recurrent anterior dislocation and functional outcomes in patients presenting with a first-time dislocation (FTD) over a 24-month period.
Diagnosis and Main Inclusion Criteria	
 1. Patients ages 14-40 years; 2. Diagnosis of post-traumatic first-time anterior shoulder dislocation having occurred within the past 3 months; 3. Provision of informed consent.
Treatment Groups	
 1. Arthroscopic stabilization (intervention group) 2. Non-operative management (control group)
Length of Follow-Up	Participants will be followed for 24 months post-treatment. Outcomes will be assessed at 6 weeks, (± 7 days), 6 months (± 30 days), 12 months (± 30 days) and 24 months (± 60 days) post-treatment.
Sample Size	50 participants

1.0. INTRODUCTION

1.1. An Unsolved Problem with Over \$1 Billion in North American Health Care Costs

The shoulder is the most commonly dislocated joint in the body with a global incidence that ranges from 15 to 25 per 100 000 people¹⁻³ and is the most common reason for surgical referral in the young active patient⁴. It is estimated that over 85,000 dislocations occur in North America annually, with a maximum incidence rate (47.8 per 100,000 person-years [95% confidence interval (CI), 41.0 to 54.5]) occurring in those between the ages of 20 and 29 years^{1,3}. Anterior dislocations, the most common type of shoulder dislocation, are often complicated by subsequent instability and recurrent dislocation, with reported rates as high as 42%¹. The estimated annual societal cost in North America due to first-time shoulder dislocations (FTDs) exceeds \$1.2 billion CAD^{1,5}.

1.2. The Anatomy of the Shoulder Dislocation

The shoulder joint, also called the glenohumeral joint, is a ball and socket joint stabilized by a number of structures including the capsule, ligaments, and a cartilaginous lining known as the labrum. Most commonly, shoulder dislocations happen anteriorly (>90%) and are due to a traumatic event (95%) from a violent external rotation of the arm in an abducted position. When the shoulder dislocates anteriorly, there is an injury to the anterior-inferior glenoid labrum, a critical stabilizing structure of the shoulder. This is known as a Bankart lesion^{6,7}. Biomechanical data confirms that injury to the anterior-inferior labrum results in significantly decreased joint translation forces⁸. Despite relocation of a dislocation, recurrent instability (partial or complete dislocations) often persists and results in further damage to cartilage surfaces of the humerus and glenoid^{9,10}. While the immediate focus in any dislocated joint is an expeditious re-location of the joint, definitive management varies among surgeons. Some prefer early surgical intervention to repair and stabilize the torn labrum, while others prefer non-operative care (short period of immobilization with early rehabilitation).

1.3. Recurrent Dislocations Have Devastating Impacts on Pain, Function and Quality of Life

By far, the most feared complication following a dislocation is a re-dislocation. Recurrent instability, experienced as a partial or complete dislocation of the humeral head from the glenoid socket post-initial dislocation, can reach upwards of 85%¹¹. Re-dislocation and continued instability results in decreased quality of life, shoulder pain, kinesiophobia and decreased physical activity and sport, as well as substantially increased costs over initial dislocation¹²⁻¹⁴. Recurrence mainly occurs in the first 2 years after the first anterior shoulder dislocation event, and 83% of patients who develop recurrent instability by 5 years do so within the first 2 years of a dislocation event¹¹. Surveys of patients demonstrate that 4 of 10 desire definitive treatment to limit further instability events and prefer surgery as their treatment of choice^{12,13}.

In addition to the health care costs of a dislocation, a prospective study of 257 patients followed for 25 years found that even if a patient does not sustain a subsequent complete re-dislocation, the presence of subtle instability can result in further labral tearing, cartilage injury, and glenoid and humeral bone erosion, which may increase the risk of developing arthritis. This is of critical concern to young active patients in whom this injury is most prevalent¹⁴.

1.4. Rationales for Early Versus Delayed Surgical Intervention

Following the initial urgent management and relocation of a dislocated shoulder, the prevention of recurrent instability is the critical management consideration for health care providers and

surgeons. Two initial management options exist in patients with a FTD: non-operative care or surgical stabilization.

Non-Operative Care (Secondary Surgical Stabilization, if needed)

The current standard of care for the vast majority of FTDs is aggressive non-operative treatment with a brief period of immobilization (around 3 weeks) followed by a physiotherapy shoulder strengthening protocol¹⁵. Failure of non-operative management with a recurrent dislocation remains the indication for surgical stabilization or if there are further complaints of instability¹⁶. Proponents of this approach argue that approximately half of patients are adequately treated by non-operative methods alone without additional risks of surgery^{17,18}. Additionally, physicians and patients involved in seasonal sports often prefer non-operative treatment to allow a quick return to play and avoid ending the sporting season with a surgical procedure, despite the potential risk of increased instability. A cohort study by Shanley *et al.* found that 85% of athletes treated non-operatively following a shoulder dislocation returned to pre-injury sport for an entire season without a recurrent instability event¹⁹. Utilizing available risk stratification tools, those advocating for this approach believe that patients at high risk of recurrent instability – younger, involved in contact sports, or with subtle bony injury - are identified appropriately and the remainder can be treated non-operatively²⁰.

Primary Surgical Stabilization

Surgeons who prefer primary surgical stabilization of a FTD argue the following:

1. Evidence for early non-operative treatment is inconclusive;
2. Recurrent instability rates are unacceptably high;
3. Outcomes (shoulder stability and functional scores) following primary stabilization are superior to those of stabilization with recurrent instability;
4. Delay in treatment results in further injury to the joint, and;
5. Early surgical intervention more cost effective than initial non-operative management.

Recent research and available evidence over the past 10 years have called into question the role of a delayed approach to managing FTDs for a number of reasons. Surgical management has been suggested as a more reliable option to prevent further dislocations and improve patient outcomes when compared with non-operative management. Arthroscopic soft tissue repair (Bankart repair) has become increasingly popular given advancements in surgical technique allowing for a minimally invasive and reliable improvement in shoulder stability with a low risk of complication. The high recurrence rate in younger patients may justify offering surgical treatment after the first dislocation episode. A recent systematic review by Hurley *et al.*¹⁶ found arthroscopic Bankart repair resulted in a 7-fold lower recurrence rate and a higher rate of return to sport and activity than non-operative management²¹. While other surgical stabilization options exist, including non-anatomic bony transfer (Latarjet procedure), the Bankart repair is widespread as it is minimally invasive and restores native anatomy.

Recent data also suggests that patients who are surgically treated following a FTD have improved outcomes when compared to those who have recurrent instability events before undergoing surgery. Marshall *et al.*²² found an increased rate of instability in patients initially treated non-operatively in comparison to those undergoing surgery immediately after a FTD (Odds Ratio (OR) = 4.14) as well as an increased odds of requiring further surgical procedures (OR=6.01). Fox *et al.*²³ similarly found rates of recurrent dislocations were 3-fold higher in those undergoing surgery after two dislocation events in comparison to a single dislocation (42.8% vs. 14.2%, p=0.03). Such

findings raise significant concern with current widespread practice of non-operative care after an initial dislocation event.

Delayed management of shoulder instability results in further injury to the shoulder joint. MRI evaluation of individuals who were assessed greater than 6 months from the time of initial dislocation had increased prevalence of not only recurrent shoulder instability events but a greater incidence and severity of intra-articular injury, including SLAP tears, labral tears, and glenoid cartilage damage²⁴.

2.0 STUDY AIMS AND OBJECTIVES

Prior to a large trial, we will conduct a pilot trial comparing arthroscopic soft tissue stabilization (intervention group) vs. non-operative management (control group) on recurrent dislocation rates and functional outcomes over a 24-month period.

2.1. Primary Questions

We aim to examine the feasibility of a larger trial comparing surgical intervention vs. non-operative management for a first-time shoulder dislocation. Feasibility objectives include:

1. Ability to recruit patients across multiple clinical sites;
2. Ability to follow patients for 24 months;
3. Ability to operate on patients within 3 months following enrollment; and
4. Assessment of crossovers.

2.2 Secondary Questions

The secondary objectives of the pilot trial will be the clinical objectives of the definitive trial:

1. Rates of recurrent shoulder dislocations up to 24 months' post-treatment;
2. Symptoms of instability without dislocation up to 24 months post treatment;
3. Clinical outcomes measured by Western Ontario Shoulder Instability (WOSI) Index, American Shoulder and Elbow Society (ASES) score, Shoulder Activity Scale, EQ-5D, Visual Analog Scale (VAS) Pain Score, and Patient Satisfaction questionnaire;
4. Physical examination: range of motion, strength, stability;
5. Return to previous level of activity and work, and;
6. Safety, shoulder-related complications and serious adverse events.

Hypothesis: We believe that the pilot trial will be feasible in our ability to recruit participants rapidly and meet our feasibility objectives.

3.0. TRIAL DESIGN

We propose a multi-centre pilot RCT to compare the effect of arthroscopic soft tissue stabilization (Bankart procedure) and non-operative treatment (physical therapy) in patients with a post-traumatic anterior FTD. Eligible and consenting participants will be followed-up by the site for 24 months. Outcomes will be assessed at 6 weeks, 6 months, 12 months, and 24 months post-treatment. Since the decision between surgery and conservative management may be heavily influenced by patient preference, we will also embed a prospective non-randomized cohort within this RCT to capture all patients who would be eligible for the study but refuse to be randomized. These patients will choose to either undergo arthroscopic stabilization or non-operative management to treat their FTD and will be followed the same way as the randomized cohort (Figure 1). This study design not only ensures maximal participation but is also more generalizable to the real world where preferences might play a role in shared decision-making.

[figure not shown]

Figure 1. Trial Design Overview

4.0. METHODS

4.1. Study Setting

This pilot trial will be conducted at a number of clinical sites across Canada, USA, South America and Europe. This study will be coordinated at McMaster University by the Department of Surgery Clinical Trials Unit who will be responsible for trial oversight, clinical site management, data management, data analysis, and knowledge dissemination.

4.2. Eligibility Criteria

Patients who meet the eligibility criteria outlined below are to be included in the study.

The inclusion criteria are:

1. Patients ages 14-40 years;
2. Diagnosis of first-time anterior shoulder dislocation having occurred within the past 3 months, confirmed either by radiographic evidence or documented reduction of anterior shoulder dislocation as well as physical examination eliciting unwanted glenohumeral translation with reproduction of symptoms;
3. Provision of informed consent.

The exclusion criteria are:

1. Patients that cannot undergo surgery or anesthesia;
2. Patients with concomitant injuries (rotator cuff tear, fracture);
3. Previous shoulder surgery;
4. Patients that will likely have problems with maintaining follow-up or are incarcerated;
5. Epilepsy/seizure disorder
6. Pregnancy;
7. Diagnosis of multidirectional instability;
8. Bony glenoid defect (bony Bankart) >10% as measured on preop imaging;
9. Dislocation without trauma, in a context of hyper laxity or atraumatic instability;
10. Cases involving litigation or workplace insurance claims (e.g. WSIB).

4.3 Recruitment Strategy and Patient Screening

Participating centers will identify patients with a FTD through outpatient clinics. The surgeon, designated fellow, or resident will conduct a history and physical examination as per standard of care. Standard radiographs must be obtained as part of this assessment.

Patients who are potentially eligible based on history and examination will be invited to participate in the trial. If they agree, written informed consent will be obtained. To obtain informed consent, study personnel will adhere to the following procedures:

- Present study information in a manner that is understandable to the patient;
- Discuss the study with the patient and answer any questions they have;
- Allow the patient ample time to discuss participation with their family/significant others, and treatment team;
- Confirm that the patient understands the risks and benefits of participating in the study and that their participation is voluntary;
- Complete the consent process and obtain signatures from the patient and site investigator or delegate.

The process of obtaining and documenting informed consent forms will be completed in accordance with local Good Clinical Practice guidelines. Participants may withdraw their consent at any time. The pilot trial will exam the feasibility of recruitment and determine the proportion of patients who are eligible after screening, refusal rates, and reasons for declining participation.

Consenting minors: Sites that will be enrolling minors should follow their local REB guidelines for consenting minors.

4.4. Group Allocation

For participants who agree to be randomized, eligible and consenting patients will be randomized using an online web-based randomization system (REDCap electronic data capture (EDC)). Randomization will be stratified by centre and will employ randomly permuted block sizes. A statistician who is otherwise uninvolved in the trial will generate the randomization list and program the randomization system. Eligible participants will be randomized in 1:1 manner to one of two treatment groups:

- Arm 1: Arthroscopic stabilization
- Arm 2: Non-operative management

Participants who agree to participate in the non-randomized arm of the study will not be randomized. Their treatment preference will be noted at baseline.

4.4.1. Blinding

The patient and the study team including the treating surgeon and study coordinator cannot be blinded as they will be undergoing/performing the procedure and/or will have access to post-operative imaging and clinical notes. Outcome assessors and study statisticians, however, will be blinded.

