4. Physical examination (range of motion and stability): Physical examination following surgery will be performed by the operating surgeon or an assigned delegate and will consist of functional assessment important to patients. Range of motion and shoulder stability are commonly reported outcome measures in the literature when assessing success following shoulder instability surgery^{30,31}. Range of motion will be assessed in forward flexion, abduction, ER and IR. Stability will be assessed primarily via the apprehension- relocation physical examination maneuver which has demonstrated the highest sensitivity in the literature for the diagnosis of anterior instability³². Presence of apprehension will be elicited by bringing the patient's shoulder into a position of 90° of abduction and 90° of external rotation in either the supine or upright position. A positive exam finding is the subjective feeling of impending subluxation or dislocation when in this provocative position. Relocation test is performed, positive test is resolution of feeling of impending subluxation.
5. Return to previous level of activity/sport and work: This outcome will be patient reported at each follow up visit. Time to return to sport will be based on when the patient is cleared by their treating surgeon to return. Time to return to work will reflect duration of work stoppage, if applicable. Specific dates of return to sport/work will be collected on study CRFs.
6. Safety: Rate of major and minor shoulder-related complications and serious adverse events.

Note: Feelings of recurrent instability or re-dislocation, regardless of group allocation and timing of onset, will be considered a treatment failure.

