4.10.1. Follow-Up Visits

Participants will be followed for 24 months post-treatment. All outcome data will be collected at 6 weeks (± 7 days), 6 months (± 30 days), 12 months (± 30 days) and 24 months (± 60 days) post-treatment at regularly scheduled clinic visits. Of note, the first follow-up timepoint (6 weeks) is relative to the initiation of rehabilitation for both groups, i.e. 6 weeks from the date of the first physiotherapy visit. At each time point, participants will complete the WOSI, Shoulder Activity Scale, EQ-5D, VAS pain score, Patient Satisfaction Scale and ASES. Physical examination (PE) will be performed by the operating surgeon or assigned delegate. Shoulder-related adverse events and SAEs will also be documented. In cases where the participant does not return to the clinic or in-person visit is not viable, study personnel will contact the participant by telephone or email. The study questionnaires can be completed by the patient online, through REDCap EDC or by telephone. A missed follow-up form should be completed if the participant misses the follow up visit. An early withdrawal form should only be completed if the participant withdraws their consent. The Schedule of Events (Table 1) details the requirements and procedures for each visit.

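### Section 4.4.1 promises blinded outcome assessors, but the protocol's own procedures contradict this for the physical examination and time to return to sport, and support it for no other outcome

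*Protocol*

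**What the plan says.** Section 4.4.1 first names those who will know the allocation: "The patient and the study team including the treating surgeon and study coordinator cannot be blinded". It then adds, without exception or procedure: "Outcome assessors and study statisticians, however, will be blinded".

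Section 4.9, item 4, defines the range-of-motion and stability outcome and names the examiner: "Physical examination following surgery will be performed by the operating surgeon or an assigned delegate". Section 4.10.1 repeats this for the follow-up visits: "Physical examination (PE) will be performed by the operating surgeon or assigned delegate". The stability test is read from what the patient feels: "A positive exam finding is the subjective feeling of impending subluxation or dislocation when in this provocative position".

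Section 4.9, item 5, covers return to activity, sport and work. It says "This outcome will be patient reported at each follow up visit", then "Time to return to sport will be based on when the patient is cleared by their treating surgeon to return", and finally "Specific dates of return to sport/work will be collected on study CRFs". Time to return to work is defined separately, by how long the participant was off work.

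**The concern.** Blinded assessment is a standard protection against detection bias, and an ethics board or a risk-of-bias assessor will give credit for it when a protocol states it. Here the surgeon who operated may measure range of motion and conduct the apprehension-relocation test, and an unblinded surgeon's decision sets the time to return to sport. Both leave room for judgement. If the procedures do not deliver the stated blinding, the trial report will claim a protection that it lacked.

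Examiner identity may also differ by arm. Table 1 schedules the examination for all participants, but a control participant who has had no operation has no operating surgeon. That participant must be examined by someone else, while a surgical participant may be examined by the person who operated.

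Section 2.2 makes these secondary outcomes the clinical objectives of the definitive trial, so an unclear blinding scheme could carry over into it.

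**Working it through.** No formula applies, and the protocol gives no figure to reproduce. The check traces each of the six secondary outcome groups in section 4.9 to its named source and compares that source with the unblinded roles in section 4.4.1.

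| Outcome group (4.9) | Source or assessor named | Against the blinding statement |
|---|---|---|
| 1. Recurrent dislocation | None named; recorded at follow-up visits (Table 1) | Unsupported (silent) |
| 2. Instability symptoms | Patient | Unsupported; patient openly unblinded |
| 3. Questionnaires, pain, satisfaction | Patient; forms administered by the coordinator or a delegate (4.9), with online or telephone completion when there is no clinic visit (4.10.1) | Unsupported; patient openly unblinded |
| 4. Physical examination | Operating surgeon or delegate (4.9, 4.10.1) | Contradicted when the operating surgeon examines; open when a delegate does |
| 5. Return to activity, sport and work | Patient; time to return to sport set by the treating surgeon's clearance | Contradicted for time to return to sport |
| 6. Safety | None named; documented at visits | Unsupported (silent) |

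Counts:
- Groups with a described blinded assessor: 0 of 6.
- Groups tied to an unblinded person, or allowing one: 4 of 6 (groups 2 to 5).
- Groups where a staff role conflicts directly with the statement: 2 of 6 (group 4, and group 5 for time to return to sport only).
- Groups that rest on the patient's report: 2 of 6 (groups 2 and 3).
- Groups with no assessor named: 2 of 6 (groups 1 and 6). Together, 2 + 2 + 2 = 6.

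A blinded assessor might be provided elsewhere in the protocol. The only other body called blinded is the Steering Committee (4.13.1), whose tasks are protocol review and solving problems in the conduct of the pilot, not judging outcomes. No adjudication committee or independent examiner is described.

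The statisticians' half of the sentence is a separate matter. Nothing in section 5 or elsewhere contradicts it.

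**The case against.** The strongest reply is that both passages on the examination allow a delegate, who could be blinded. The protocol does not exclude that, so a reader who concludes that the blinding statement is simply false goes too far. This stands. The statement is contradicted where the operating surgeon examines and unsupported where a delegate does.

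A reader might also take 0 of 6 to mean that all six outcome groups are shown to be assessed unblinded. The protocol does not support that. For recurrent dislocation and safety it names no assessor, and silence is not contradiction. Instability symptoms and questionnaires come from patients whom 4.4.1 openly calls unblinded, so a sentence about assessors conflicts with them only if the patient counts as the assessor. Likewise, the operating surgeon does not alone judge apprehension, because a positive finding is the patient's own sensation.

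On return to sport, a reader might infer that item 5 contradicts itself by being both patient-reported and set by clearance. These can be two measures: whether the patient has returned to the previous level, and the time to return. Nor does the protocol say that the dates on the case report form are patient-reported dates of actual return; the sentence before suggests that the sport date could be the clearance date. What stands is an ambiguity, and the fact that the timing depends on an unblinded role.

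Finally, the primary outcomes are recruitment, follow-up, surgery within 3 months and crossovers, and section 5.2 treats the secondary outcomes as exploratory and without p-values. This limits the impact. One link to the primary outcome remains: under section 4.8, control-arm surgery counts as a crossover only if the participant has had no feelings of instability and no re-dislocation. The feelings are patient-reported, so blinding an examiner would change this count little.

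**Conclusion.** The concern holds in limited form. The assessor-blinding statement in 4.4.1 conflicts with 4.9 and 4.10.1 on the physical examination and with 4.9 on time to return to sport. It has no support for the other outcomes, and blinding of the statisticians is untouched.

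The conclusion assumes that the unqualified phrase in 4.4.1 covers whoever examines the participant and whoever determines time to return to sport. The protocol offers no narrower reading.

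The size of any bias cannot be derived from the protocol. The consequence is moderate: exploratory comparisons could be misread as blinded, and the scheme could pass unexamined into the definitive trial. The conflict does not invalidate the pilot's feasibility assessment.

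**What to change.** Reconcile the passages in one of two ways:

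- (a) Restate 4.4.1 so that patient-reported outcomes, the physical examination and return to sport are described as open-label, and only the statisticians as blinded.
- (b) Keep the intent by using the delegate option already allowed. Require the examiner to be someone other than the operating or treating surgeon and, where feasible, unaware of allocation. Name in 4.4.1 the outcomes that this covers and describe the rest as open-label. A delegate who did not operate is not blinded for that reason alone, so both conditions need stating.

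In either case, record on the case report form who performed each examination. Under (b) this also shows how often a separate examiner was achieved, which is useful to know before the definitive trial.

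As a secondary point, state whether the return-to-sport date on the form is the actual return or the clearance, and record the two separately. Time to return to work is not tied to clearance and needs no change here.

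Option (a) costs only a change of wording; option (b) also needs a suitable delegate at each site. Recording the examiner and the second date adds two items to the form. Neither option needs more participants, visits or analyses. The downside is that the stated protection against bias becomes less favourable than the present text suggests.
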